3 STUDY PURPOSE AND OBJECTIVES

3.1 Primary Objective

Retifanlimab Cohort

- To assess the efficacy of the combination of enoblituzumab + retifanlimab, based primarily upon evaluation of Investigator-assessed ORR in the response evaluable patient population, in patients with recurrent or metastatic SCCHN not curable by local therapy, with no prior systemic therapy for SCCHN in the recurrent or metastatic setting (with the exception of systemic therapy completed > 6 months prior if given as part of multimodal treatment for locally advanced disease).

Tebotelimab Cohort

- To assess the safety, tolerability, and preliminary efficacy of the combination of enoblituzumab + tebotelimab, based primarily upon evaluation of Investigator-assessed ORR in the response evaluable patient population, in patients with recurrent or metastatic SCCHN not curable by local therapy, with no prior systemic therapy for SCCHN in the recurrent or metastatic setting (with the exception of systemic therapy completed > 6 months prior if given as part of multimodal treatment for locally advanced disease).

3.2 Secondary Objectives

Retifanlimab Cohort

- To evaluate the Investigator-assessed PFS, disease control rate (DCR), DoR, and OS.
- To evaluate safety and tolerability.
- To assess the PK of enoblituzumab + retifanlimab.
- To evaluate the immunogenicity of enoblituzumab + retifanlimab.

Tebotelimab Cohort

- To evaluate the Investigator-assessed PFS, DCR, DoR, and OS.
- To assess the PK of enoblituzumab + tebotelimab.
- To evaluate the immunogenicity of enoblituzumab + tebotelimab.

3.3 Exploratory Objectives

Retifanlimab and Tebotelimab Cohorts

- To explore the relationships between PK, pharmacodynamics, patient safety, and antitumor activity.
- To explore PPK and exposure-response analyses.
- To explore the relationships between PD-1, PD-L1, B7-H3, and LAG-3 expression on tumor cells and response.
- To investigate the immune-regulatory activity in vivo, including various measures of T-cell and NK-cell activation/exhaustion in peripheral blood and/or tumor biopsy specimens.
- To assess circulating immune cells and effect of treatment.
- To evaluate peripheral biomarkers and correlate with potential clinical response.
- To explore gene expression profiles and Fc receptor polymorphism in PBMCs and/or pre-treatment tumor biopsies and correlate with clinical response (when applicable).

The results of the exploratory objectives may not be included in the Clinical Study Report or database lock unless they represent meaningful findings.

4 STUDY DESIGN

[figure not shown]
4.1 Overall Study Design

This is a Phase 2, open label, non-randomized study in the first-line treatment of patients with recurrent or metastatic SCCHN not curable by local therapy, with no prior systemic therapy for SCCHN in the recurrent or metastatic setting (with the exception of systemic therapy completed > 6 months prior if given as part of multimodal treatment for locally advanced disease). The study will be conducted at approximately 35 centers in approximately 5 countries.

Approximately 80 patients will be enrolled in 2 cohorts, to receive enoblituzumab in combination with either retifanlimab (Retifanlimab Cohort, PD-L1 positive [CPS \geq 1] patients, N=50) or tebotelimab (Tebotelimab Cohort, PD-L1 negative [CPS < 1] patients, N=30; see [Figure 5](#)). Enrollment into each cohort will occur independently in a non-randomized fashion. Patients may not crossover between cohorts. PD-L1 expression will be prospectively collected and prospectively analyzed as described in [Section 10.2.1](#). B7-H3 and LAG-3 expression will be prospectively collected and retrospectively analyzed.

An independent Data Safety Monitor (DSM), the Sponsor, and Investigators will maintain regular oversight of patient safety throughout the trial. In the Tebotelimab Cohort, toxicity will be evaluated by monitoring the occurrence and severity of DLTs (see [Section 4.2](#)) in the first 12 patients (2 mini-cohorts of 6 patients each) through Cycle 2 Day 7. If warranted, enrollment in the Tebotelimab Cohort will be paused and ad hoc meetings with the Principal Investigators (or designee), the Medical Monitor, and the independent DSM will be held to consider dose reduction of tebotelimab to 300 mg, Tebotelimab Cohort termination, or continuation at the pre-established 600 mg dose.

Figure 5 Study Schema

Enrollment in the 2 study cohorts will occur independently in a non-randomized fashion

Dosing Regimens:

Enoblituzumab: 15 mg/kg Q3W
Retifanlimab: 375 mg Q3W
Tebotelimab: 600 mg Q3W

[figure not shown]
Efficacy Outcomes

Primary: ORR
Secondary: PFS, DCR, DoR, OS

The data for each of the Retifanlimab and Tebotelimab Cohorts will be analyzed upon completion of enrollment of each cohort, and after all patients in the applicable cohort have at least one tumor assessment, to inform whether to proceed with the study and to determine any modifications to the trial design.

Patients will receive the assigned study drugs (enoblituzumab 15 mg/kg and either retifanlimab 375 mg or tebotelimab 600 mg) on a Q3W basis, in cycles of 3 weeks duration (see [Figure 6](#)). The initial tumor assessment will occur at the end of Cycle 2 (i.e., after approximately 6 weeks), and at the end of every 3 cycles thereafter (i.e., approximately every 9 weeks). After receipt of the last dose of study treatment, patients will enter an Efficacy Follow-up Period and will be followed for survival.

Figure 6 Treatment Cycles

Study treatment will continue in cycles of 3 weeks duration until confirmed CR (except as noted below), disease progression, unacceptable toxicity, withdrawal of consent, physician recommendation to discontinue therapy, death, or the maximum allowed treatment duration has been reached (see [Section 4.4](#) for a complete list of reasons for discontinuation of treatment). The maximum allowed treatment duration is 35 cycles for each study drug.

Discontinuation of study treatment may be considered for patients who have attained a confirmed CR. However, until Cycle 33, 2 additional cycles of study treatment may be completed beyond the date of confirmed CR (the total number of cycles of study treatment must not exceed 35).

Patients who have radiographic progression may remain on study treatment until the next scheduled radiographic evaluation if the following conditions are met: absence of clinical symptoms or signs indicating clinically significant disease progression; no decline in ECOG performance status; absence of rapid disease progression or threat to vital organs or critical anatomical sites (e.g., central nervous system [CNS] metastasis, respiratory failure due to tumor compression, spinal cord compression) requiring urgent alternative medical intervention; and no significant, unacceptable, or irreversible toxicities related to study treatment.

4.2 Dose Limiting Toxicity (Tebotelimab Cohort)

For the purposes of safety management and defining DLTs, the combination of enoblituzumab + tebotelimab will be treated as one entity. If a DLT is considered related to study treatment, no distinction will be made as to which agent is the causative agent and administration of both agents will be stopped.

Dose limiting toxicities will be based on treatment-emergent drug-related AEs (or laboratory abnormalities) occurring through Cycle 2 Day 7.

Patients in the Tebotelimab Cohort who experience DLT will discontinue study treatment.

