and decreased appetite, pneumonitis (6.8%, each); lymphocyte count decreased (6.0%); and events of chills, anemia, and pruritus (5.3% each). Greater than or equal to Grade 3 TRAEs were reported in 38 patients (28.6%). Of these, the most commonly reported in $\geq 5\%$ of patients were IRR (7.5%) and lipase increased (6.0%). The majority of \geq Grade 3 AEs of lipase increased were isolated, reversible, and asymptomatic. The majority of IRR were Grade 1 or 2 in severity. Observed IRR to date have been manageable and have resolved without sequelae. Patients who experienced Grade 3 IRR have fully recovered following brief interruption in dosing and after receiving treatment based upon symptomatology. Typically, these IRR occurred only with the first dose of enoblituzumab and did not recur with subsequent dosing.

Twenty-three patients (17.3%) experienced serious adverse events (SAEs) considered related to enoblituzumab + pembrolizumab; for the majority of these patients (20/23, 87%), the events were \leq Grade 3 in severity. The most common SAEs considered related were IRR (7.5%) and pneumonitis (4.5%). Fourteen patients (10.5%) experienced at least 1 \geq Grade 3 SAE that was considered related to enoblituzumab + pembrolizumab; with the exception of IRR (7 patients, 5.3%) and pneumonitis (3 patients, 2.3%), the events were singularly reported.

Myocarditis and pneumonitis have been identified as important potential risks associated with enoblituzumab/pembrolizumab combination treatment. The cumulative safety data reviewed to date suggest the combination with enoblituzumab does not increase the risk of myocarditis or pneumonitis compared to anti-PD-1 inhibitors alone. Notably, both important potential risks are recognized, yet rare, adverse effects associated with the administration of PD-1 inhibitors. Furthermore, pneumonitis and myocarditis have not been observed in MacroGenics-sponsored monotherapy trials of enoblituzumab to date.

Study CP-MGA271-03 – Enoblituzumab + Retifanlimab Combination Therapy

This open-label study is evaluating the safety, tolerability, and DLT of 15 mg/kg enoblituzumab in combination with a flat dose of 375 mg of retifanlimab, each administered IV Q3W. Enrollment in the enoblituzumab + retifanlimab cohort is complete (N=12).

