The majority of TRAEs observed in Dose Escalation have been mild-to-moderate in severity (i.e., Grade 1 or Grade 2). A total of 14 (26.4%) patients treated in Dose Escalation have had at least one \geq Grade 3 TRAE. These events include lipase increased (n=3); fatigue and IRR (n = 2 each); and adrenal insufficiency, amylase increased, arthritis, colitis, diarrhea, hypophosphatemia, immune-mediated hepatitis, myalgia, pancreatitis, pruritus, rash, transaminases increased, and vomiting (n = 1 each). Additionally, 1 patient treated in the limited hepatocellular carcinoma dose escalation at 120 mg experienced Grade 4 asymptomatic events of amylase and lipase increased with no clinical or radiographic evidence of pancreatitis. No patients have experienced a Grade 5 TRAE.

A total of 13 (24.5%) patients experienced SAEs in Dose Escalation. Seven (13.2%) patients had at least 1 treatment-related SAE, including immune-mediated hepatitis (n = 2, 400 mg and 1200 mg); adrenal insufficiency with resultant hypotension (n = 1, 400 mg), anemia (n = 1, 400 mg), colitis (n = 1, 800 mg), hypophosphatemia (n = 1, 400 mg), pancreatitis (n=1, 1200 mg), and thyroiditis (n=1, 600 mg). SAEs assessed not to be related to tebotelimab include abdominal pain, clostridium difficile colitis, diarrhea, dyspnea, hemobilia, hyponatremia, inappropriate antidiuretic hormone secretion, pneumonia, pulmonary hemorrhage, pyrexia, small intestinal obstruction, and urinary tract infection. These events were related to the respective patient's underlying malignancy or comorbid condition(s).

The dose of 600 mg, given Q2W or Q3W, was chosen for further development in the Cohort Expansion Phase. This decision was based on the totality of clinical, PK, and receptor occupancy data. Within Dose Escalation, tebotelimab demonstrated acceptable tolerability.

The MTD was not defined or exceeded, and 1200 mg represents the maximum dose level to be administered in Study CP-MGD013-01.

Study CP-MGD013-01 – Tebotelimab Monotherapy – Cohort Expansion

A total of 210 patients with advanced cancer have been treated with tebotelimab 600 mg Q2W or Q3W. Of these patients, 187 (89.0%) experienced at least one AE, irrespective of attribution. Common AEs, reported in $\geq 15\%$ of patients, include fatigue (26.7%), anemia (15.7%), and nausea (15.2%).

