4.2.1 Hematologic Dose Limiting Toxicity

Hematologic DLT is defined as follows:

- Grade 4 neutropenia lasting > 5 days
- \geq Grade 3 febrile neutropenia
- Grade 4 thrombocytopenia, irrespective of duration
- Grade 3 thrombocytopenia associated with clinically significant bleeding
- \geq Grade 3 hemolysis

The following events will be specifically excluded from the definition of hematologic DLT:

- \geq Grade 3 lymphopenia
- Grade 3 anemia that is not associated with other clinically significant complications.

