4.2.2 Non-hematologic Dose Limiting Toxicity

- Any intolerable Grade 2 toxicity that results in dose interruption lasting more than 20 days, or requires drug withdrawal.
- Non-hematologic DLT is defined as any \geq Grade 3 non-hematologic event with the following exceptions:
 - Grade 3 electrolyte abnormality that lasts less than 72 hours, that is not otherwise associated with clinical complications, and responds to medical intervention
 - Grade 3 fever that lasts < 72 hours and is not associated with hemodynamic compromise
 - Grade 3 nausea or vomiting that lasts < 72 hours and responds to medical intervention
 - Grade 3 amylase and/or lipase elevation that is not associated with either clinical or radiographic evidence suggestive of pancreatitis.
 - Grade 3 gastrointestinal AEs of diarrhea, constipation, abdominal pain, cramping, dyspepsia or dysphagia that resolves to \leq Grade 1 within 14 days with medical therapy

- Grade 3 fatigue that lasts < 7 days
- Grade 3 infusion related reaction or cytokine release syndrome that lasts < 12 hours and responds to medical intervention.
- Grade 3 or 4 endocrinopathy that is adequately controlled with hormone supplementation
- Grade 3 skin toxicity that resolves to \leq Grade 2 within 14 days of initiation of corticosteroids
- Grade 3 inflammatory reaction (e.g., with associated pain, swelling) attributed to a local antitumor response (e.g., inflammatory reaction at sites of metastatic disease, lymph nodes, etc.) that resolves to \leq Grade 2 within 7 days.

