4.2.3 Hepatic Non-hematologic Dose Limiting Toxicity

Hepatic non-hematologic DLT will be defined as follows:

- Any elevation of one or more transaminases $> 8 \times$ the institutional upper limit of normal (ULN) irrespective of duration.
- Any Grade 3 elevation of one or more transaminases $> 5.0 - 8.0 \times$ the ULN that does not resolve to Grade 2 within 7 days, and Grade 1 or baseline within 14 days. If steroids are administered, they must be tapered to ≤ 10 mg of prednisone or equivalent per day by Day 14. Please see [Section 7.2.2](#) for further management guidelines.
 - For patients with Grade 1 or 2 elevations of transaminases at baseline, a doubling of transaminases will be considered dose limiting, if not resolved to baseline within 14 days.
- Any Grade 3 elevation of total bilirubin that is $> 5 \times$ the ULN irrespective of duration.
- Any elevation of total bilirubin $> 3.0 - 5.0 \times$ ULN that does not resolve to Grade 2 within 7 days and Grade 1 or baseline within 14 days. If steroids are administered, they must be tapered to ≤ 10 mg of prednisone or equivalent per day by Day 14. Please see [Section 7.2.2](#) for further management guidelines.
- Any event meeting the criteria for Hy's law as follows (all three features):
 - Aspartate aminotransferase (AST) and/or alanine aminotransferase (ALT) $> 3 \times$ ULN, or doubling of AST and/or ALT for patient having Grade 2 transaminase levels at baseline.
 - Concurrent elevation of total bilirubin $> 2 \times$ ULN without initial evidence of cholestasis
 - No alternative etiology can be identified.

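### Tebotelimab DLT run-in: one scheduled post-dose safety lab in the whole DLT window, so short silent laboratory DLTs can go unseen; draws at the existing Day 8 and Day 15 visits would close most of the Cycle 1 gap

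*Protocol*

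**What the plan says.** Protocol Section 4.2 sets the window and includes laboratory findings: "Dose limiting toxicities will be based on treatment-emergent drug-related AEs (or laboratory abnormalities) occurring through Cycle 2 Day 7". It also sets the consequence: "Patients in the Tebotelimab Cohort who experience DLT will discontinue study treatment". Section 4.1 applies this monitoring to the first 12 patients, in two groups of six; SAP Section 3.1 repeats the window and adds no laboratory schedule.

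Several laboratory DLTs have no duration element:
- Section 4.2.1: "Grade 4 thrombocytopenia, irrespective of duration".
- Section 4.2.3: transaminases above 8 times "the institutional upper limit of normal (ULN) irrespective of duration"; total bilirubin above 5 × ULN, also regardless of duration; and the Hy's law combination.
- Section 4.2.2 exempts "Grade 3 amylase and/or lipase elevation that is not associated with either clinical or radiographic evidence suggestive of pancreatitis". The exemption names Grade 3 only, so a silent Grade 4 enzyme rise reads as a DLT.

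Appendix 1 puts the clinical laboratory tests at screening, Day 1 of each cycle and the end-of-treatment visit. Footnote h lets the Day 1 sample be taken up to 3 days early. Section 9.8 has safety labs reviewed before dosing, with other tests done as the clinical situation requires. Cycle 1 Days 2, 3, 8 and 15 are clinic visits for PK, ADA and biomarker samples only, and Appendix 3 already takes blood at each of them.

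**The concern.** The DLT definitions ask whether an abnormality occurred at any time up to Cycle 2 Day 7. The schedule can answer that only for abnormalities still present at one moment, about three weeks after the first dose. Symptomatic events will prompt unscheduled tests. A silent platelet or liver abnormality will not, and if it has returned to about Grade 1 or normal by Cycle 2 Day 1, nothing scheduled will show that it happened.

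The stake is at patient level: someone who met a DLT criterion, and should stop both drugs, receives a second dose. The documents present no clinical data for enoblituzumab + tebotelimab together, so these 12 patients are the protocol's first look at the pair. Elsewhere the protocol treats weekly testing as the right interval: Section 7.2.2 requires liver tests at least weekly for three weeks when treatment resumes after a Grade 3 hepatic elevation.

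**Working it through.** The plan states no detection rate for the run-in, so there is no figure of its own to reproduce.

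**Inputs**
- First dose on Day 1. Cycle length 21 ± 3 days (Appendix 1, footnote a), so Cycle 2 Day 1 is Day 22 nominally, and Day 19 to Day 25 at the limits.
- The safety draw may be up to 3 days before that dose (footnote h), so it falls between Day 16 and Day 25.
- Day 8 and Day 15 visits have ± 1 day windows (Appendix 1).
- Nominal end of the DLT window: Cycle 2 Day 7 = Day 28.
- Earliest onset is taken as Day 2.

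**Step 1: number of scheduled post-dose draws in the window.** The Cycle 1 Day 1 labs precede the first dose, Days 2 to 15 have no safety panel, and the Cycle 2 Day 1 labs precede the second dose. The count is one, with none in the week after the second dose. A delayed Cycle 2 dose (Section 4.3.1) or an early end-of-treatment visit can add one.

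**Step 2: longest event that fits wholly before a draw on Day x.** It runs from Day 2 to Day x − 1, so its length is x − 2 days.
- Nominal, x = 22: 20 days.
- Dose on Day 22, sample 3 days early, x = 19: 17 days.
- Dose on Day 19, sample 3 days early, x = 16: 14 days.
- Dose and sample on Day 25, x = 25: 23 days.

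The range is 14 to 23 days.

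**Step 3: the same with Day 8 and Day 15 draws.** Between draws on Days a and b the unsampled run is b − a − 1 days.
- Nominal: Days 2–7, 9–14 and 16–21, each 6 days.
- Day 8 visit on Day 7, Day 15 visit on Day 16: 16 − 7 − 1 = 8 days.
- Day 15 visit on Day 14, Cycle 2 Day 1 draw on Day 25: 25 − 14 − 1 = 10 days, the worst case.

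**Step 4: illustration only.** Assume onset equally likely on each of Days 2 to 28 (27 days), no unscheduled tests, and a draw on Day 22. An event with onset o and duration d is seen if some draw x satisfies o ≤ x < o + d. For hepatic events, d means time to about Grade 1.

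| Duration | Day 22 only | Days 8, 15 and 22 |
|---|---|---|
| 3 days | 3/27 = 11% | 9/27 = 33% |
| 7 days | 7/27 = 26% | 21/27 = 78% |
| 14 days | 14/27 = 52% | 21/27 = 78% |

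The ceiling of 78% arises because onsets on Days 23 to 28 (6/27 = 22%) follow the last draw under either schedule. If the Cycle 2 Day 1 sample is taken on Day 19, the two 78% figures become 18/27 = 67%.

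**The case against.** Severe laboratory toxicity may rarely be both silent and short. Both drugs persist: the protocol gives half-lives of 18.7 days for enoblituzumab and 8.5 days for tebotelimab, with sustained target binding at 120 mg and above. Section 7.2.2 manages severe hepatic events with steroids and sets recovery checks at 7 and 14 days, so untreated return to about Grade 1 before Cycle 2 Day 1 is possible but nowhere shown to be likely. A hepatic value still at Grade 2 at that draw would be caught and treatment held.

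The documented silent events are weak support. The patient who "experienced Grade 4 asymptomatic events of amylase and lipase increased with no clinical or radiographic evidence of pancreatitis" had hepatocellular carcinoma and received tebotelimab 120 mg, one-fifth of the dose here. The mostly reversible and asymptomatic lipase rises of Grade 3 or higher in Section 2.3.2.2 came with weekly enoblituzumab plus pembrolizumab. Neither report gives onset or duration. Prior exposure is also reassuring: tebotelimab reached 1200 mg every two weeks without defining an MTD, and was combined with margetuximab, which has the same Fc region as enoblituzumab, with acceptable tolerability.

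Finally, the remedy is partial. Two-thirds of 3-day events in the illustration are still missed, and the week after the second dose stays unsampled.

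All of this stands, and it limits the size of the point. It does not remove the mismatch between DLT criteria that ignore duration and a schedule with one draw. AE collection, clinically prompted labs and independent safety monitoring do not detect an abnormality that causes no symptoms.

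**Conclusion.** For a patient dosed on schedule, the pre-dose Cycle 2 Day 1 sample is the only scheduled post-dose hematology and chemistry draw in the DLT window. A silent laboratory DLT without a duration element, lasting up to 14 to 23 days depending on the windows, can fall wholly before it, and the patient is then redosed. Draws at Days 8 and 15 reduce that to 6 days nominally and 10 at most. The gap lengths need no assumption about event rates; the detection percentages rest on uniform onset and assumed durations. The schedule reading rests on the laboratory row of Appendix 1, footnote h and the visit label; confirm it against the laid-out table, since column alignment in the text version is unreliable.

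Two stronger readings are not supported:
- **That the 600 mg decision is compromised.** Section 4.1 has no DLT-count threshold; it says only "If warranted, enrollment in the Tebotelimab Cohort will be paused". There is no rule whose error rate could be computed.
- **That a known share of DLTs will be missed, or that safety oversight fails.** The documents give no rate or time course for short silent laboratory DLTs, and the enzyme reports are not DLT rates. Oversight continues through the other routes described.

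This is a cheap improvement in ascertainment, worth making for the 12 patients concerned.

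**What to change.** For the 12 DLT-monitored patients, add the Appendix 2 hematology and serum chemistry panels, reviewed locally, to the Cycle 1 Day 8 and Day 15 columns of Appendix 1. The chemistry panel already includes ALT, AST, bilirubin, amylase and lipase.

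Cost: 12 × 2 = 24 extra panels, as added tubes at visits where blood is already drawn, and a minor amendment with IRB/IEC approval (Section 16.1). No new visit is needed. The downside is that more laboratory DLTs may be observed, and so more patients stopped under Section 4.2. Cycle 2 Day 1 to Day 7 remains without a further scheduled draw, because no visit exists there; covering it would mean adding one, which is not proposed here.
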